
Other exploratory analyses. ***Other Outcomes:*** We will use the framework described above for alcohol outcomes to analyze other behavioral outcomes (cannabis, NMPDU). ***Moderation:*** To assess potential moderators (e.g., sex, age) we will include interactions with treatment group in the GLMM models above. ***Mediation:*** To test if alcohol motives and other variables (e.g., mental health) mediate treatment effects, we will use Imai's causal mediation analysis framework, implemented in the R package *mediation*. Traditional mediation analysis is limited by the class of statistical models (e.g. the linear structural model of Baron and Kenny) that can be accommodated. Under technical assumptions of sequential ignorability, mediation effects are identifiable using Imai's framework when models for the mediator and outcome are non-linear, have discrete or continuous outcomes, include random effects, or are non-parametric. ***Engagement:*** Counts from Snapchat message logs (e.g., content viewed, replies), will be assessed descriptively to see types of content with high response and to measure dose. We will test for sex and age differences in engagement. ***Cost:*** We will calculate summary statistics for the total intervention-specific costs and mean costs per participant, with confidence intervals. Costs will be reported with/without start-up and development, for example, including costs for recruiting and training coaches and clinical supervision. As with [name] prior work, net costs (savings) will be calculated by subtracting mean costs per participant in the control group from costs per participant for the assigned condition, also calculating the incremental cost effectiveness ratio (difference in mean intervention cost vs. control divided by difference in mean effectiveness between intervention and control). Change in health benefits will be quantified as the difference in alcohol consequences per month for the

intervention vs. control, expressed in dollars per consequence averted. Sensitivity analyses to evaluate alternate assumptions for estimated costs will be conducted. Given likely skewness, we will identify appropriate ways to generate confidence intervals that do not rely on a normal distribution (e.g., non-parametric boot-strapping).

Power Analysis.

For exploratory analyses regarding intervention efficacy, our inferential target (the regression coefficient corresponding to treatment group) is effectively equivalent to the comparison of two means, for which Cohen's D is the typical effect size (0.2: small; 0.5: medium; 0.8: large). Under the expected sample size ($n = 50-52$ per group), we will have sufficient power ($>80\%$) to detect effects on outcomes at a single time point if $D > 0.56$, a medium effect size. In analyses involving multiple follow-ups, the effective sample size cannot be smaller than the nominal sample size ($n = 50-52$ per group), and so the effect size of $D = 0.56$ is conservative in that case.

12. Provide the study stopping rules part of the study protocol. Generally, stopping rules reflect one of the following conditions: 1) there is clear evidence of harm; 2) there is no likelihood of demonstrating treatment benefit (futility); 3) there is overwhelming evidence of the benefit of treatment.

The PI will work directly with NIAAA, in the case that project discontinuation is necessary. Should there be clear evidence of harm to the participants due to this trial we will cease the trial. Given this is a no more than minimal risk study as deemed by our IRB, we do not anticipate evidence of harm. As this is a pilot/feasibility trial, we may not be able to detect a treatment effect and thus do not anticipate stopping the trial due to evidence of futility or benefit.

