From the pool of eligible and verified participants, study staff will select participants to receive an invitation to continue to the next part of the study (baseline). Screening items will be used to select participants representing a variety of characteristics (e.g., gender, race/ethnicity) to ensure that the intervention is widely acceptable among individuals in the study's target age group. Selected, verified participants will be invited to view and agree to the RCT consent in Qualtrics, followed by an online baseline survey. Selected participants will receive an email containing a link to the consent and baseline survey in Qualtrics. Participants who indicate that email is not their preferred method of communication will receive a text/social media notification (depending on their preferred contact method) directing them to the email with their consent and survey link. We will send reminders via different contact methods (e.g., email, private message on social media, text) to encourage completion of this survey and completion of study enrollment.

Those who complete baseline measures will be randomized to their assigned condition for 8 weeks, and will later be asked to complete a 2-month post-test after the active intervention period, and a 4-month outcomes assessment. Compensation at baseline will be a \$35 electronic gift card (e.g., Amazon.com, Target, etc.) for participants who complete all baseline activities. Compensation will be a \$35 electronic gift card for the 2-month post-test and a \$40 electronic gift card for the 4-month follow-up.

Inclusion/Exclusion Criteria. For screening, participants must: be age 18-25, reside in the U.S., be able to read English, view, and click on a social media ad. Eligibility criteria for baseline and randomization is self-reported past-month HID (using an item based on MTF¹⁴⁴) and regular Snapchat use (at least 3 days/week). Participants will be excluded if they fail identity verification (see prior studies^{132,133}) based on: 1) IP addresses, 2) survey time completion, 3) repeat attempts, and 4) survey responses. Aim 1 participants are excluded from Aim 2.

Randomization and Consideration of Key Biological Variables. Randomization to conditions will be balanced based on sex and age (18-20, 21-25 years) using urn randomization in blocks of 4. After completing the baseline survey, participants will be informed which condition (intervention, control) they were randomized into via Qualtrics.

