Intervention condition. Overview: Participants randomized to the intervention will be initially provided with a link to the NIAAA's guide Rethinking Drinking website, a list of national resources located on our study website, and the study's Snapchat user safety agreement. Participants in the intervention group will be instructed on how to add our study's account as a Snapchat contact. Participants will be invited to accept the friend invite from our study account. Participants may be contacted by a study team member via phone, email, or their preferred method of communication to aid them in adding peer coaches on Snapchat. Once we confirm participants as contacts, peer coaches will send a test/welcome "snap" to confirm the connection. They will also be directed to an orientation video (up to 3 mins) that provides an introduction to how *SnappyHour* works (e.g., frequency and types of "snaps"/ stories to expect, duration, coach availability),

introduces peer coaches, and notes that coaches are not available 24/7 and in the event of crisis the participants should contact 911 or the crisis text line (text “HOME” to 741741). Pre-selected intervention content will be sent to participants up to 7 days a week on Snapchat. Snapchat involves 2-way messaging; when participants in the intervention condition reply to messages, coaches will discuss content, in a MI-consistent manner using reflections, open ended questions, and affirmations to participants during their scheduled shifts.

Intervention Content. Participants will receive pre-selected snaps (e.g., coach-initiated snaps, snapchat stories, engagement cues) up to 3 times per day (with the number and type varying across days to increase novelty), from peer coaches over 8 weeks. Based on our Aim 1 pilot work, we have revised our plan and content for the intervention. Sample content based on iterative participant feedback is available in the uploaded “Aim 2 Snapchat Messaging Description”. A variety of snaps and stories will be used to prompt participants to review and discuss intervention themes (see Table 1) and to promote engagement. Snaps and stories sent by coaches include a variety of multi-media messages (pictures, text, gifs, videos, links to articles or coping exercises with screenshots, etc.). The initial content is stored in a content library accessible to staff, but wording will be tailored to the individual participant, consistent with motivational interviewing (MI)

Table 1. Intervention Themes

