Our content involves MI consistent coach greetings that are consistent with the Why/How model of MI. Peer-coaches will encourage discussion of content by eliciting discussion around theoretically-determined intervention topics shown above. Snaps will also be used to encourage engagement. Coaches will reply to comments with MI strategies (e.g., reflection, affirmation), including managing sustain talk (e.g., come alongside, agree with a twist), and eliciting protective behavioral strategies for drinking less. Messages address 1) Why (evoking reasons for change), and/or How (Tools for change). Based on our ongoing cannabis intervention on Snapchat, we have developed a peer coach guidelines outlining basic MI principles, protocols for posting, risk assessment, and peer-coach professionalism. We have also revised the User Safety Agreement from our cannabis Snapchat intervention (HUM00139068) for use in this study which outlines guidelines for participants (e.g., privacy, no snapping opportunities to buy or receive drugs with peer-coaches; no racial or political slurs, respect and confidentiality). Once participants in the intervention group are informed of the group they are randomized to, they are directed to a Qualtrics page containing the User Safety Agreement and they will be sent an additional copy of it via email. Snaps will be monitored during the 8-week period by scheduled peer-coaches who can contact rotating on-call supervisors (all highly experienced in MI) who

[figure not shown]

Figure 3. Snapchat screenshot of messages received/opened

include the investigators, study coordinator, and our lab network of clinical post-docs, and clinical social workers, who work as a team across studies address potential participant risk situations. We will note in the orientation video that we cannot monitor snaps 24/7, and include crisis numbers.

Tracking Engagement with Intervention Content.

Coaches will track messages in an electronic log, noting whether snaps were known to be viewed (Fig. 3 shows messages sent/opened) and types of content discussed to quantify engagement. Coaches monitor Snapchat to determine if messages were viewed and send periodic reminders (e.g., via SMS) to prompt engagement when messages go unopened; these messages will be recorded on a log.

Coach Responses and Risk Management.

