Control condition: Control participants will be provided with a link to and be asked to review NIAAA's guide Rethinking Drinking.¹⁴⁵ Additionally, participants will be provided with a list of national resources located on our study website. To balance receipt of this information across groups, we will provide the intervention condition participants with a link to review Rethinking Drinking at baseline as part of study resources.

Follow-Up Procedures. Self-report surveys will be self-administered online via Qualtrics at 2-month post-test (\$35 compensation) and at the 4-month follow-up (\$40 compensation). Assessment reminders will be sent in a variety of ways, which may include via e-mail, private Snapchat messaging, SMS text message, mail and/or phone call and other social media, based on contact information participants provided in their

screening survey.

Study Measures. Whenever possible we will use reliable and valid measures from prior studies with emerging adults (Table 1).

Screening survey. To assess study eligibility and characterize the study sample, participants will be asked about their demographics, social media involvement, and health behaviors, including alcohol use. The screening survey should last 5 minutes.

Baseline and Follow-up Assessments. Participants will be asked to self-report measures including demographics; SM use; alcohol expectancies, consequences, and motives; protective strategies, etc. Although trial outcomes focus on feasibility and acceptability, the main behavioral dependent measures of interest for related to the intervention are alcohol consumption (e.g., HID episodes, daily drinking questionnaire, AUDITC) and alcohol-related negative consequences. Other measures include: age and sex as potential moderators; and peer influences, risk perceptions, discounting rate mental health symptoms as potential mediators; and feasibility/acceptability (adapted from prior work). The baseline and follow-ups are expected to last 30-40 minutes. The 2- and 4-month surveys will mirror the baseline survey measures with the inclusion of acceptability measures at 2-months and removal of baseline measures of intervention topic preferences and strengths and goals which can be used by peer coaches to tailor intervention content.

Data Management and Analysis

Please see Aim 2 Data Analysis Plan in the DSMP below.

Human Use Considerations and Protections (Aims 1 and 2)

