Participants could potentially experience emotional discomfort as a result of being asked very personal questions or because of intervention content. Because the study takes place solely online via mobile devices and computers, all eligible and verified participants will receive crisis/referral information as part of the emailed informed consent and via a national resource listing from the study's website that will be linked for all participants at baseline and at 2- and 4-month assessments. Intervention participants will be made aware during consent, in the User Safety Agreement, and in the study introduction video that coaches will be "snapping" in shifts and thus may not be available in the event of a crisis. On the closing page of each survey they will be reminded of crisis hotlines/text-lines and national substance abuse and mental health resources should they experience discomfort that they wish to address with a professional. The electronic resource page on the website (sent to all participants at baseline and assessments) will include national resources including suicide hotlines/text-lines, mental health and substance use treatment, etc. Our prior

studies have involved phone and web-based follow-ups; thus, we will use established protocols for addressing any crisis or harm situations that may arise, including having national hotline phone and text numbers. If a participant shares specific information about their own dangerous behaviors (e.g., driving impaired, self-harm), we will privately message them to express concern, provide safety plans, and discuss referral information, using protocols established in our prior and ongoing work.

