Participants will be informed that we will take steps necessary to secure their data. Online data collected as part of screening and baseline assessments and analysis of intervention interactions will also be stored in secure, password-protected databases on the secure U-M network. Participants will be instructed at the close of each web-based survey (e.g., screening, baseline, post-test, follow-up) of steps they can take to further protect their privacy (e.g., clear browser history). In Aim 2, peer coaches sharing content via Snapchat will do so in private spaces using privacy screens where others who are not part of the research team could not see the data. Study cell phones and iPads (which have apple encryption) used to send and store Snapchats will have strong password protection and will only be accessed by study staff in private locations.

These risks will be noted as a possibility in the informed consent document with a statement encouraging participants to not leave their mobile devices or computers open/unlocked (i.e., they will be encouraged to use a passcode), and not to leave study webpages open and viewable when not using them. In addition, to limit inadvertent disclosure of participation in the study to family or others, we will suggest that participants use strong passwords (mix of upper/lower case letters, numbers, symbols) on their mobile devices and email accounts that they give the study for contact. Further, participants will choose how they wish to be contacted by the study for surveys and reminders (e.g., email, text message, social media messages) and in any of these contacts we will not include sensitive information about substance use.

Protections Against Risks

To minimize the risk of violating confidentiality, RAs will make every effort to ensure that study data are always kept confidential. Research staff will sign a pledge of confidentiality. Staff training procedures will include information about the importance of confidentiality and techniques to maintain confidentiality of all information reported by research participants. Staff will maintain human subjects and confidentiality certifications through the U-M Program for Education and Evaluation in Responsible Research and Scholarship system and will complete CITI Good Clinical Practice Training. Consent documents will fully explain the study procedures, potential risks, and potential benefits.

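### The protocol presents choice of contact channel as a privacy safeguard, but its procedures make email unavoidable for the baseline survey and allow reminders by channels the participant did not choose

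*Combined protocol and SAP*

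**What the plan says.** The safeguard is in the Potential Risks section, in the paragraph on limiting accidental disclosure to family or others: "participants will choose how they wish to be contacted by the study for surveys and reminders". Its examples are email, text and social media messages. The same sentence adds that "in any of these contacts we will not include sensitive information about substance use". Item (b) of the parental-consent waiver argument, under Human Use Considerations and Protections, also says that people who continue can name a preferred contact method.

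The contact procedures are elsewhere:

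- **Aim 1 and Aim 2 recruitment procedures.** Selected participants are emailed a link to the consent and baseline survey. Those who do not prefer email are notified by text or social media, "directing them to the email with their consent and survey link". Reminders for this survey go out by different methods.
- **Intervention condition (Aim 2).** For help with the Snapchat set-up, "Participants may be contacted by a study team member via phone, email, or their preferred method of communication".
- **Follow-Up Procedures (Aim 2).** Besides email, reminders may go by "private Snapchat messaging, SMS text message, mail and/or phone call and other social media", according to the contact details the participant gave.
- **Intervention Content (Aim 2).** For the User Safety Agreement, intervention participants are told that "they are directed to a Qualtrics page containing the User Safety Agreement and they will be sent an additional copy of it via email".
- **Potential Risks.** A separate paragraph says "all eligible and verified participants will receive crisis/referral information as part of the emailed informed consent".

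**The concern.** A participant who reads the risk section would expect that naming text messages as the contact channel keeps study surveys out of a shared or visible inbox, off the home phone and out of the post. The procedures do not work that way. Preference decides only who gets an extra notice; the email goes out regardless.

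This matters because breach of confidentiality is the first risk the protocol lists. The sample reports high-intensity drinking, and ages 18-20 form a whole randomization stratum. A safeguard offered to participants and to the ethics board should describe what staff will do.

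**Working it through.** No formula applies, and the plan gives no figure to reproduce. The check sets the safeguard beside each procedure.

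**1. Scope of the safeguard.** The choice of channel covers contacts for surveys and reminders. The sentence on substance-use content refers back to those same contacts.

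**2. Procedures within that scope.**

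| Contact | Channel in the procedures | Follows the participant's choice? |
|---|---|---|
| Consent and baseline survey link | Email to all selected; other channels only point to the email | No |
| Baseline reminders | Several methods, not tied to the preferred one | Not assured |
| 2-month and 4-month reminders | Any supplied detail, including mail and phone | Not assured |

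The first row is a direct contradiction. It is a survey contact, and the text provides expressly for people who said email was not their preference, yet still emails them. In the other two rows the procedures permit channels the participant did not choose. Mail and phone are not among the examples in the risk section.

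**3. Procedures outside that scope.** The Snapchat set-up contact is optional help, and the emailed User Safety Agreement is a copy of conduct rules. Neither is a survey or a reminder, so neither contradicts the sentence.

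**4. Content.** The recruitment section describes an email holding a link. No section says that a survey or reminder message names alcohol or drugs. The reference to an emailed informed consent is looser and could mean the consent text itself. However, the recruitment section has the consent viewed in Qualtrics, and Human Use Considerations makes it the opening pages of the survey. Shorthand for the emailed link is therefore a fair reading.

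**5. Reach.** The email rule applies to all selected participants, so to all 102 in the Aim 2 target and to others invited who do not enrol. The same wording governed up to 50 in Aim 1. The share who do not prefer email is not given. Purely as an illustration, an assumed 10% to 40% would be 0.10 × 102 ≈ 10 to 0.40 × 102 ≈ 41 trial participants. The contradiction does not depend on this range.

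**The case against.** The strongest reply is that nothing goes to an address the participant did not supply. Follow-up channels are limited to details provided, the email account is one given for contact, and a preferred method is not a veto on other methods. The risk section also advises strong passwords on devices and on those email accounts, and says the risks are noted in the consent. The consent pages and the contact form are not available for review; they may already say that email is used, or already accept several channels.

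Much of this stands, and it limits how far the point can go. It does not remove the mismatch. The risk section speaks of choosing, not of preferring. Contact details are collected partly for identity verification, so supplying a number or address is not the same as accepting it as a channel. Passwords do not protect posted mail or a call that someone else answers. Whatever the consent says, the protocol sections still disagree with one another.

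A reader might infer three stronger things, which the documents do not support:

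- **That the no-content assurance is broken.** No survey or reminder contact is shown to carry substance-use information. The User Safety Agreement does include the rule "no snapping opportunities to buy or receive drugs with peer-coaches", but it falls outside the contacts that assurance covers, and it is a rule of conduct rather than information about anyone's own use.
- **That participation will be disclosed to family.** This is a residual risk, which the protocol recognises and partly mitigates. It is not a demonstrated consequence.
- **That the parental-consent waiver fails.** That argument concerns the effect of requiring parental consent, and it applies only to participants below the age of majority in three states.

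**Conclusion.** The point holds in a narrow form. The channel-choice safeguard in Potential Risks is contradicted by the recruitment procedures, which email the consent and baseline link whatever the stated preference. It is not assured by the reminder procedures, which allow any supplied channel.

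The email contradiction reaches every selected participant. How many would object is unknown. The conclusion rests on the protocol text alone and assumes that the unseen consent and contact form do not resolve it. The point concerns confidentiality wording and procedure; it has no bearing on sample size, randomization, outcomes or analysis. It is worth correcting because the correction is cheap and makes a stated protection true.

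**What to change.** For Aim 2:

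1. Have the contact form ask participants to tick every channel they accept for study contact, separately from details given only for verification.
2. Send the consent and survey link itself, in neutral wording, through a ticked channel.
3. Limit baseline, 2-month and 4-month survey reminders to ticked channels.
4. If email must remain mandatory, correct Potential Risks to say that email is required and that other supplied channels may be used, and tell participants so before they give contact details.
5. Align the wording on the emailed informed consent with the recruitment section, so that both describe an emailed link rather than consent text.
6. Keep the emailed User Safety Agreement for those who accept email, and add a save or print option on its Qualtrics page for the others. The Agreement tells participants that coaches may be unavailable in a crisis, so everyone should be able to keep a copy.

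The cost is one multi-select item and some wording edits. The drawback is fewer reminder routes for some people, which could slightly reduce response at 2 and 4 months. Allowing several ticks limits that loss.
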